#### **9.2.2.2 Medication Satisfaction Questionnaire (MSQ)**

The MSQ is a patient-rated scale designed and validated to assess the patient's satisfaction with his or her current antipsychotic medication. The MSQ consists of one item that is rated on a 7-point scale ranging from 1 (extremely dissatisfied) to 7 (extremely satisfied). The patient can complete the MSQ without any training.

It takes less than 1 minute to complete the MSQ.

#### **9.2.2.3 Tolerability and Quality of Life questionnaire (ToolL)**

The ToolL is a patient-rated scale developed to measure the impact of side-effects on the quality of life in patients treated with antipsychotic medication. The ToolL consists of eight domains: mood (worry-upset), function capabilities, fatigue-weakness, weight gain, stiffness-tremor, physical restlessness, sexual dysfunction and dizziness-nausea. Each domain is rated on a 4-point scale from 1 (no impact) to 4 (maximum impact). Total scores range from 8 (no impact) to 32 (maximum impact).

It takes approximately 5 minutes to complete the ToolL.

### **9.2.3 Health Care Resource Utilisation**

The Health Economic Assessment (HEA) questionnaire will be used to collect resource utilisation. The HEA will be provided in English only. Country specific version will be used for US and Canada. Instructions on how to complete the scale will be provided to the site.

The HEA is a questionnaire aiming at monitoring patients' health care resource utilisation such as physicians' visits, outpatient and inpatient services and other relevant services. Site personnel involved in the conduct of the study must ask these questions to the patients at selected visits. This allows for relating cost data to clinical efficacy and safety, and these data may be used for cost-effectiveness analyses.

The HEA is available in a Baseline Evaluation version which is to be used at the Baseline Visit and a Follow-Up Evaluation version which is to be used at Primary Outcome/Withdrawal Visit.

It takes approximately 15 minutes to complete the HEA.

### 9.3 Pharmacokinetic Assessments

Blood samples for IMP quantification (2 mL per time point) will be drawn in 2 mL K3 EDTA tube in accordance with [Panel 2](#). The blood sampling and handling procedures are described in the study-specific *Laboratory Specification Manual*.

Sampling time point and sampling date should be recorded. At the visits for PK assessments, the time point and date of the latest intake of study medication should be recorded and the patient should be asked about the usual time of study medication intake during the period since the last visit.

The blood samples will be analysed for Lu AF35700 and Lu AF36152 using an analytical method validated in accordance with the EMA *Guideline on Bioanalytical Method Validation* and the FDA *Guidance for Industry*.

If other metabolites are identified and considered significant, these may be included in an exploratory analysis. The bioanalysis will be performed by the Department of Bioanalysis, H. Lundbeck A/S. A bioanalytical protocol will be prepared by Lundbeck before the plasma samples are analysed.

The result of the analysis will not be reported back to the investigator.

### 9.4 Translational Medicines Assessments (For *Other Patients* only)

#### 9.4.1 General Considerations

Although the possible future exploratory biomarker analyses will help to increase our understanding of the aetiology of schizophrenia and the molecular basis of the drug response, the efforts described in this protocol are strictly research based. Therefore, as the complex interactions between genes and disease are currently not characterised to a level that translates to a meaningful clinical advantage, individual results from the exploratory biomarker analyses will not be given to the patients. For the same reasons, individual results will not be added to the patients' medical records.

The patients will have no direct benefit from the exploratory biomarker analyses. As blood sampling for the exploratory genomics, proteomics, and metabolomics is an integral part of the study, the main *Patient Information Sheet* covers these analyses. Conversely, blood sampling for the possible future genetic biomarker analysis is optional and a separate *Patient Information Sheet* covers this analysis.

The blood samples for biobanking and possible future exploratory biomarker analysis, or the data derived from these blood samples, may be shared with academic and public institutions and other companies. However, Lundbeck will retain full control of the samples and their use in accordance with the information in the *Patient Information Sheet* and a Material Transfer

Agreement. Furthermore, the results based on the analysis of the samples may be pooled across studies to increase the statistical power of the analyses.

A patient and/or his or her legal representative (if applicable) may, at any time and without stating a reason, specifically request the destruction of the patient's exploratory biomarker sample, irrespective of his or her continued participation in the study. The investigator must send a written request on behalf of the patient to the international study manager. The investigator will receive written confirmation from Lundbeck when the sample has been destroyed.

The blood samples for genomics, proteomics, and metabolomics will be single-coded using the patient's screening number. The blood samples for genetic biomarker analysis will be double-coded as described in EMA's position paper on pharmacogenetic terminology to ensure patient privacy protection.

The results of the possible future pharmacogenetics, proteomics/metabolomics and gene expression profiling will not be reported to the investigator.

#### **9.4.2 Blood Sampling for Gene Expression Profiling**

Blood samples for gene expression profiling (RNA) will be collected in two PAXgene tubes (2,5 mL) at each time point. The maximum volume of blood to be collected during the study for this purpose will be 10 mL. Samples for gene expression profiling will be shipped to a Central Laboratory, United States, for sample storage and possible preparation and analysis.

The result of the analysis will not be reported back to the investigator.

Only the patients not previously participating in a study investigating Lu AF35700 will have blood drawn for gene expression profiling.

#### **9.4.3 Blood Sampling for Metabolomic/Proteomic Biomarkers**

Blood samples for metabolomic/proteomic biomarkers will be collected in one 10 mL K2 EDTA tube at each time point. The maximum volume of blood to be collected during the study for this purpose will be 20 mL. The samples for metabolomic/proteomic biomarkers will be shipped to a Central Laboratory, United States, for sample storage.

Only the patients not previously participating in a study investigating Lu AF35700 will have blood drawn for metabolomics/proteomic biomarkers.

#### **9.4.4 Blood Sampling for Pharmacogenetics**

It is optional for the patient to donate a blood sample for exploratory pharmacogenetic analysis. A blood sample (9 mL) will be collected in K3 EDTA tubes for subsequent DNA extraction. Blood tubes will be shipped on dry ice to a Central Laboratory, United States, where DNA will be extracted and retained. DNA aliquots will be shipped to a Central

Laboratory, for storage. The genetic variants to be analysed may include single nucleotide polymorphisms (SNPs) and copy number variations (CNVs). The analytical methods may be polymerase chain reaction (PCR), qPCR (quantitative PCR), sequencing, or whole genome scans on microarrays.

The results of these analyses are not specifically related to this study. The sample will be stored at a Central Laboratory, United States.

Only patients not previously participating in a study investigating Lu AF35700 will have blood drawn for pharmacogenetic analysis.

## **9.5 Safety Assessments**

### **9.5.1 Adverse Events**

The patients will be asked a non-leading question (for example, “how do you feel?”, “how have you felt since your last visit?”) at each visit, starting at the Screening Visit. Adverse events (including worsening of concurrent disorders, new disorders, and pregnancies) either observed by the investigator or reported spontaneously by the patient will be recorded, and the investigator will assess the seriousness and the intensity of the adverse event and its relationship to the IMP. Results from relevant tests and examinations, such as clinical safety laboratory tests, vital signs, and ECGs, or their corresponding conditions will also be recorded as adverse events if considered by the investigator to be clinically significant.

See chapter [10](#) for further information on adverse events.

### **9.5.2 Clinical Safety Laboratory Tests**

The clinical safety laboratory tests are listed in [Panel 4](#).

**Panel 4 Clinical Safety Laboratory Tests**

Haematology	Livera	Kidneya
B-haemoglobin	S-total bilirubin	S-creatinine
B-erythrocyte count	S-conjugated bilirubin	S-urea nitrogen (BUN)
B-haematocrit	S-alkaline phosphatase (AP)	S-uric acid
B-MCV	S-alanine aminotransferase (ALT)	Urine (dipstick)
B-MCHC	S-aspartate aminotransferase (AST)	U-protein (dipstick)
B-total leucocyte count	S-lactate dehydrogenase (LDH)	U-glucose (dipstick)
B-neutrophils (% of total leucocytes)	S-γ-glutamyl transferase (γGT)	U-blood (dipstick)
B-eosinophils (% of total leucocytes)	Electrolytesa	U-ketones (dipstick)
B-basophils (% of total leucocytes)	S-sodium	Urine drug screenc
B-lymphocytes (% of total leucocytes)	S-potassium	U-Amphetamine
B-monocytes (% of total leucocytes)	S-chloride	U-Barbiturates
B-thrombocyte count	S-bicarbonate	U-Benzodiazepines
P-INR (prothrombin ratio)	S-calcium (total)	U-Cannabinoids
Lipidsa	Endocrine and Metabolica	U-Cocaine
S-cholesterol (total) (fasting)	S-albumin	U-Methadone
S-triglycerides (fasting)	P-glucose (fasting)	U-Opiates
S-low density lipoprotein (LDL)	S-prolactin b	U-Phencyclidine
S-high density lipoprotein (HDL)	B-HbA1c (fasting)	Pregnancy (women only)
	S-total protein	S-hCG
		Urine dipstick d
		Additional Test
		S-Creatine phosphokinase (CPK) e

B – blood; P – plasma; S – serum; U – urine

- Clinical chemistry
- Result will remain blinded
- Urine samples will be collected and analysed at the site using dipsticks
- Can be repeated at any time during the study at the discretion of the investigator. All positive urine pregnancy test results must be confirmed by a serum test.
- S-troponin T, reflex for CPK >500U/l.

Blood samples for the clinical safety laboratory tests will be collected as outlined in [Panel 2](#). The blood sampling and handling procedures are described in the study-specific *Laboratory Specification Manual*.

The blood samples will be analysed at the central laboratory.

The investigator must review (initial and date) the results of the clinical safety laboratory tests as soon as possible after receipt of those results. Out-of-range values must be interpreted by the investigator as “not clinically significant” or “clinically significant” with a comment concerning the planned follow-up. Tests for clinically significant out-of-range values must be

repeated, or an appropriate clinical follow-up must be arranged by the investigator and documented on the laboratory report, until the value has stabilised or until the value has returned to a clinically acceptable value (regardless of relationship to IMP). Any value that is out-of-range at the Primary Outcome or Withdrawal Visit and judged clinically significant must be followed according to accepted medical standards for up to 42 days or until the value normalises or stabilises or a diagnosis or reasonable explanation has been established. Any out-of-range values followed after the last protocol-specified contact with the patient will be documented in the patient's medical record.

Clinically significant out-of-range values must be recorded as an adverse event on an *Adverse Event Form*.

The central laboratory will be notified by the sponsor when the biological samples may be destroyed.

### **9.5.3 Vital Signs**

Pulse rate and blood pressure will be measured using a standard digital meter.

Pulse rate and blood pressure will be measured in the following order: supine, sitting, and standing after the patient has rested in each position for at least 3 minutes.

Vital signs must be assessed prior to blood sampling.

Abnormalities of clinical significance must be recorded as an adverse event on an *Adverse Event Form*.

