### 1.1.5.3 Safety

The main body of safety data in patients with schizophrenia comes from the MAD study (study 14754A) which has been completed. The other study in patients with schizophrenia, the ongoing PET study (study 15859A), is still blinded.

In the MAD study, the adverse events with the highest incidence (>10%) in the Lu AF35700 groups in the daily dosing cohorts were: somnolence (33%), anxiety (23%), headache (21%, placebo level), orthostatic hypotension (19%), dizziness (16%), psychotic disorder (14%), and akathisia (11%). In the once-weekly dosing cohorts the adverse events occurring in

≥2 patients in the Lu AF35700 groups were (number of patients out of 12): somnolence (5), constipation (4), insomnia (3), anxiety (2), and musculoskeletal pain (2). In total there was 1 serious adverse event, increased psychosis, which necessitated hospitalisation of the patient. The patient recovered after 9 days after treatment with paliperidone. The investigator assessed the causality as *not related* to the investigational medicinal product (IMP). All non-serious adverse events were of *mild* to *moderate* intensity, with the exception of one event of *severe* somnolence which resolved after a few hours. The blinded data from the ongoing PET study showed that anxiety, insomnia, and headache have been reported as adverse events in that study.

Please refer to the *Investigator Brochure* for a summary of the TEAEs with the highest incidence in MAD study 14754A.

In the MAD study, an explorative analysis of the effect of treatment on QTcf indicated a treatment and dose-related trend for QTcf prolongation. None of the patients in the study had any symptoms or QTcf values that met the potentially clinically significant (PCS) criterion (>500 ms or >60 ms increase from baseline) and no observations from ECG or cardiac telemetry were reported as adverse events.

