12.4 Vital Signs and Weight

The PCS criteria used for vital signs and weight are the Lundbeck standard PCS criteria described in SOP_09978: *PV – PCS and standard reference values for laboratory investigations, vital signs and ECGs in clinical studies*, version 6, and are also included in [Table 2](#).

Descriptive statistics for the body measurements (weight, BMI, and waist circumference) in the Treatment Period, both absolute values and changes from baseline, will be presented by variable and week and the last assessment in the Treatment Period. The summaries for the absolute values will also include summaries for Baseline.

Descriptive statistics for the vital signs parameters, both absolute values and changes from baseline, will be presented by test and week and the last assessment in the Treatment Period. The summaries for the absolute values will also include summaries for baseline.

The number and percentage of patients with at least one PCS low value or PCS high value at any post-baseline assessment in the Treatment Period will be summarized by vital signs and body measurement parameter. All available assessments in the period will be included in the evaluation of PCS.

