S-LDL cholesterol, fasting	LDL	mmol/L		≥ 4.9
S-HDL cholesterol, non-fasting/unknown	HDL	mmol/L	≤ 0.8	
S-HDL cholesterol, fasting	HDL	mmol/L	≤ 0.9	
Cardiac/Skeletal/Muscle				
S-creatinine kinase (total)	CK	IU/L		≥ 400 (women) ≥ 750 (men)
S-creatinine kinase MB isoenzyme	CKMB	µg/L		≥ 8.5 or
	CKMBCK	%		≥ 3.5% of total CK
S-lactate dehydrogenase (total)	LDH	IU/L		≥ 750
S-troponin I	TROPONI	µg/L		≥ 1.5
S-troponin T	TROPONT	µg/L		≥ 0.4
Infection				
S-C-reactive protein	CRP	mg/L		≥ 25
S-globulin (total)	GLOBUL	g/L	≤ 15	≥ 55

Laboratory Test	CDISC Term	Unit	PCS Low	PCS High
Urine				
Urinary pH	PH		≤ 4	≥ 9

S=serum; B=whole blood; U=urine

Table 2 PCS Criteria for Vital Signs, Weight/BMI, and Waist Circumference

Variable	CDISC Term	Unit	PCS Low	PCS High
Waist circumference	WSTCIR	Cm	decrease ≥ 7%	increase ≥ 7%
Weight	WEIGHT	Kg	decrease ≥ 7%	increase ≥ 7%
Body Mass Index	BMI	kg/m ²	decrease ≥ 7%	increase ≥ 7%
Pulse rate, supine/sitting/unknown	PULSE	beats/min	< 50 and decrease ≥ 15	≥ 120 and increase ≥ 15
Diastolic blood pressure, supine/sitting/unknown	DIABP	mmHg	≤ 50 and decrease ≥ 15	≥ 105 and increase ≥ 15
Systolic blood pressure, supine/sitting/unknown	SYSBP	mmHg	≤ 90 and decrease ≥ 20	≥ 180 and increase ≥ 20
Orthostatic systolic blood pressure	OBP	mmHg	≤ -30	
Orthostatic pulse rate	OPR	beats/min		≥ 20
Temperature	TEMP	°C	decrease ≥ 2	≥ 38.3 and increase ≥ 2

Increase/decrease is relative to the baseline value.

Table 3 PCS Criteria for ECG Parameters

ECG Parameter	CDISC Term	Unit	PCS Low	PCS High
Absolute Time Interval				
PR interval	PRMEAN	Msec		≥ 260
QRS interval	QRS DUR	Msec		≥ 150
QT interval	QTMEAN	Msec		≥ 500
Derived Time Interval				
Heart rate	HRMEAN	beats/min	< 50 and decrease ≥ 15	≥ 120 and increase ≥ 15
QTcB interval	QTcB	Msec	< 300	> 500 or increase > 60
QTcF interval	QTcF	Msec	< 300	> 500 or increase > 60

Increase/decrease is relative to the baseline value.

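### No PCS limit applies to a standing blood pressure or pulse reading as such: SAP Table 2 evaluates standing values only as within-visit orthostatic differences

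*Protocol*

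**What the plan says.** Protocol 9.5.3 sets the measurement: "Pulse rate and blood pressure will be measured in the following order: supine, sitting, and standing after the patient has rested in each position". Panel 2 schedules vital signs at every treatment visit from Week 1 to Week 52, which is 15 post-baseline visits.

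Protocol 16.1 and SAP 4.1 make absolute values, changes from baseline and PCS values in systolic pressure, diastolic pressure and pulse part of the primary endpoint, listed separately from adverse events.

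SAP Appendix III, Table 2 labels its three absolute rows "Systolic blood pressure, supine/sitting/unknown", "Diastolic blood pressure, supine/sitting/unknown" and "Pulse rate, supine/sitting/unknown". Two further rows concern posture: "Orthostatic systolic blood pressure" and "Orthostatic pulse rate". There is no orthostatic diastolic row, and the SAP does not say which two positions form the difference.

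SAP 12.4 counts patients with at least one PCS value per parameter, using all assessments in the Treatment Period. It also says: "Descriptive statistics for the vital signs parameters, both absolute values and changes from baseline, will be presented by test and week". Position is not mentioned there. SAP 12.2 lists individual values only for patients who have a post-baseline PCS value.

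**The concern.** Each absolute row combines a level with a change from baseline, for example a systolic value of 90 mmHg or below together with a fall of at least 20. Supine and sitting readings are tested this way, and so is a reading whose position is unknown. A reading known to be standing is not. The orthostatic rows ask a different question, namely how far pressure or pulse moves between positions at one visit. They do not ask how far the standing value has moved since baseline.

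This matters for this drug. Protocol 1.1.2 describes it as an antagonist at alpha-adrenergic receptors. Protocol 1.1.5.3 reports orthostatic hypotension in 19% of daily-dosed patients on Lu AF35700 in the multiple-ascending-dose study. Low pressure on standing is therefore a foreseeable effect, and the PCS summary is the part of the primary endpoint that does not depend on an investigator judging a reading clinically significant.

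**Working it through.** The plan gives no figure for this point, so there is none to reproduce. The check has three steps.

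**1. Table 2, row by row**

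| Row | PCS low | PCS high | Does a standing reading enter? |
|---|---|---|---|
| Pulse, absolute | <50 and fall ≥15 | ≥120 and rise ≥15 | No |
| Diastolic, absolute | ≤50 and fall ≥15 | ≥105 and rise ≥15 | No |
| Systolic, absolute | ≤90 and fall ≥20 | ≥180 and rise ≥20 | No |
| Orthostatic systolic | ≤ -30 | none | Only as a within-visit difference |
| Orthostatic pulse | none | ≥20 | Only as a within-visit difference |

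**2. A patient who falls between the systolic rows** (invented values)

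Standing baseline 112 mmHg; on treatment supine 105, sitting 98, standing 88.

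- Standing level: 88 ≤ 90. Fall from standing baseline: 112 − 88 = 24 ≥ 20. The existing systolic limits would be met if they applied to standing readings.
- Supine row: 105 > 90, not met. Sitting row: 98 > 90, not met.
- Orthostatic row: supine to standing 88 − 105 = −17; sitting to standing 88 − 98 = −10. Neither is −30 or lower, so the row is not met under either derivation.

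No systolic row is breached. With a standing value of 88, the same holds for any supine value above 90 and below 88 + 30 = 118, provided sitting is also above 90. Pulse and diastolic values are not specified in the example. A pulse rise of 20 or more on standing, or a supine or sitting pulse or diastolic breach, would still bring the patient into the PCS summary under another row.

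**3. How often this might happen**

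The documents give no blood pressure distribution, so every input here is an assumption:

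- supine systolic mean 120 to 125, between-patient SD 11 to 12, visit-to-visit SD 7;
- mean standing drop on treatment 6 to 10 mmHg, with SD 3 to 6 both between and within patients;
- sitting midway between supine and standing.

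The quantity is the percentage of patients with at least one standing systolic ≤90 and a fall ≥20 from the standing baseline, and no breach of any systolic row at any visit. Pulse and diastolic were not simulated.

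| Setting | Patients missed by the systolic rows |
|---|---|
| 15 visits, no mean postural drop at baseline | about 4% to 17% |
| 15 visits, same mean drop at baseline as on treatment | about 2% to 9% |
| 8 visits, same mean drop at baseline as on treatment | about 1% to 7% |
| 15 visits, zero mean drop throughout | about 0.5% to 4% |

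The second row deserves weight. SAP 3.1 takes baseline from the last lead-in assessment, when patients were on Lu AF35700, risperidone or olanzapine, so some postural drop may already be present. The third row reflects incomplete follow-up: Protocol 5.1 planned for 200 completers out of 400. The last row shows that part of any standing count comes from variability alone.

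**The case against.** The strongest opposing case is that standing hypotension is already covered. Table 2 has two postural rows, and SAP 12.4 counts patients who meet them. Protocol 9.5.3 requires clinically significant vital-sign abnormalities to be recorded as adverse events, and SAP 12.1.6 tabulates treatment-emergent events by preferred term. The 19% from the multiple-dose study is itself an adverse-event incidence, so the route that produced that signal is retained. Table 2 reproduces the sponsor's standard criteria, and nothing in the documents says that limits set for supine and sitting readings suit standing ones.

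Most of this stands. A reader might infer that standing hypotension is counted in no table; the orthostatic rows and the adverse-event tables show otherwise. What the objection does not reach is a low standing value with a large fall from baseline and a moderate postural drop. No systolic PCS row tests for it, and the adverse-event route depends on individual judgement.

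A reader might also infer that the one-value-per-visit rule in SAP 19.2.2 removes standing readings from the PCS counts. It does not: that rule governs analyses by visit, while the PCS summary uses all available assessments. For the by-visit tables, the position labels in Table 2 imply that position is held in the data, and SAP 12.4 excludes no position. The absence of a statement that tables and selection run within position is missing detail, not evidence that standing values are dropped.

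The objection about transferring limits is fair as a caution on interpretation. It is met by reporting standing rows separately rather than merging them with the existing ones.

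**Conclusion.** The point holds as a gap in sensitivity. Standing pulse and blood pressure are collected at every treatment visit and belong to a primary endpoint, but no level-and-change PCS limit is applied to them. The PCS summary can therefore understate low standing pressure. The same gap applies to standing diastolic pressure, which has no orthostatic row either, and to standing pulse beyond the orthostatic difference.

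The size is not derivable from the documents. Over 15 visits the assumed inputs give about 2% to 17% of patients missed by the systolic rows, with the lower part of the range more relevant if a postural drop is already present at baseline. Shorter follow-up lowers it further. Some of these patients would be caught by the orthostatic pulse row or as adverse events, so these percentages are not an estimate of patients missed by the whole plan. The conclusion about Table 2 rests on its wording alone and does not depend on the simulation. It is a cheap improvement to the safety summary, not an error that invalidates it.

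**What to change.** In SAP Table 2 and the PCS summary of SAP 12.4, add separate standing rows for pulse, diastolic pressure and systolic pressure. Use the limits already in the table, take change from the standing baseline value, and report these rows beside the existing ones. No new threshold is proposed.

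In SAP 12.4 and 19.2.2, state that the by-visit and last-assessment tables, the baseline value and the choice among multiple assessments are all handled within position. The SAP already does the equivalent for fasting and non-fasting laboratory values. State also which two positions define the orthostatic differences.

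The cost is SAP wording and a few table rows, with no new data collection. Some standing values will be flagged because of visit-to-visit variability, so the reported PCS percentage will look less favourable; a footnote can say so.
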